4.4 ADVERSE EVENT REPORTING

AE reporting requirements are summarized below.

4.4.1 Definitions

Adverse Event: An AE is any untoward medical occurrence in a participant administered an investigational product or has undergone study procedures and which does not necessarily have a causal relationship with this treatment. An AE can therefore be any unfavorable and unintended sign (including an abnormal laboratory finding), symptom, or disease that is temporally associated with the use of a medicinal (investigational) product, whether or not related to the medicinal (investigational) product.

An abnormality identified during a medical test (e.g., laboratory parameter, vital sign, ECG data, physical exam) should be defined as an AE only if the abnormality meets 1 of the following criteria:

- Induces clinical signs or symptoms.
- Requires active intervention.
- Requires interruption or discontinuation of study drug.
- The abnormality or investigational value is clinically significant in the opinion of the investigator.

Serious Adverse Event: An SAE, as defined by per 21 CFR 312.32, is any adverse event that results in one of the following outcomes, regardless of causality and expectedness:

- **Results in death**
- **Is life-threatening.** Life-threatening means that the person was at immediate risk of death from the reaction as it occurred, i.e., it does not include a reaction which hypothetically might have caused death had it occurred in a more severe form.
- **Requires or prolongs inpatient hospitalization** (i.e., the event required at least a 24-hour hospitalization or prolonged a hospitalization beyond the expected length of stay). Hospitalization admissions and/or surgical operations scheduled to occur during the study period but planned prior to study entry are not considered SAEs if the illness or disease existed before the person was enrolled in the trial, provided that it did not deteriorate in an unexpected manner during the trial (e.g., surgery performed earlier than planned).
- **Results in persistent or significant disability/incapacity.** Disability is defined as a substantial disruption of a person's ability to conduct normal life functions.
- Is a congenital anomaly or birth defect; or
- **Is an important medical event when**, based upon appropriate medical judgment, it may jeopardize the participant and require medical or surgical intervention to prevent one of the outcomes listed above. Examples of such medical events include allergic bronchospasm requiring intensive treatment in an emergency room or at home; blood dyscrasias or convulsions that do not result in inpatient hospitalization, or the development of drug dependency or drug abuse.

Medical and scientific judgment should be exercised in deciding whether expected reporting is also appropriate in situations other than those listed above. For example, important medical events may not be immediately life threatening or result in death or hospitalization but may jeopardize the participant or may require intervention to prevent one of the outcomes listed in the definition above (e.g., suspected transmission of an infectious agent by a medicinal product is considered an SAE). Any event is considered a SAE if it is associated with clinical signs or symptoms judged by the investigator to have a significant clinical impact. All SAEs are to be followed up until resolved, judged to be no longer clinically significant, or until they become chronic to the extent that they can be fully characterized.

An adverse event can be Anticipated or Unanticipated:

- **Anticipated adverse events** are those that have been previously identified as resulting from the underlying disease, the HCT, or aGVHD and not related to study drug.
- **Unanticipated adverse events** are those that vary in nature, intensity, or frequency from information in the current anticipated event list, the Investigator's Brochure, the package insert, or when it is not included in the informed consent document as a potential risk. Unanticipated events would also include those that have not been previously described as a result of the underlying disease requiring HCT, the HCT or aGVHD.

4.4.2 Classification of Adverse Events by Severity

The severity refers to the intensity of the reported event. The Investigator must categorize the severity of each reportable SAE according to the NCI CTCAE Version 5.0. CTCAE guidelines can be referenced at the following website: <http://ctep.cancer.gov/reporting/ctc.html>. For any

term that is not specifically listed in the CTCAE scale, intensity will be assigned a grade of one through five using the following CTCAE guidelines:

- **Grade 1:** Mild; asymptomatic or mild symptoms, clinical or diagnostic observations only; intervention not indicated
- **Grade 2:** Moderate; minimal, local or noninvasive intervention indicated; limiting age-appropriate instrumental activities of daily living
- **Grade 3:** Severe or medically significant but not immediately life-threatening; hospitalization or prolongation of hospitalization indicated; disabling; limiting self-care activities of daily living
- **Grade 4:** Life-threatening consequences; urgent intervention indicated
- **Grade 5:** Death related to AE

4.4.3 Classification of Adverse Events by Relationship to Investigational Product

The relationship of each reported event to the study treatment will be assessed by the Investigator; after careful consideration of all relevant factors such as (but not limited to) the underlying study indication, coexisting disease, concomitant medication, relevant history, pattern of the SAE, temporal relationship to any study treatment interventions and de-challenge or re-challenge according to the following guidelines:

- **Possibly, Probably, or Definitely Related:** there is a reasonable possibility that the study treatment caused the event. A relationship of possibly, probably, or definitely related to the investigational product is considered related for the purposes of regulatory authority reporting.
- **Unlikely, or Not Related:** There is no reasonable possibility that the investigational product caused the event. An unlikely or not related relationship to the investigational product is not considered related for the purposes of regulatory authority reporting.

4.4.4 Required Adverse Event Reporting

The required adverse event reporting for the BMT CTN 2002 protocol is outlined below.

- T-Guard arm: all adverse events, including SAEs, must be reported from randomization through 30 days following the last dose of T-Guard.
- Ruxolitinib arm: all adverse events, including SAEs, must be reported from randomization through Day 44 (to align with the maximum reporting period for participants in the T-Guard arm).
- Any SAEs occurring after that period, but assessed as related to the investigational product, must be reported.
- Any unanticipated SAEs from time of enrollment through the study defined follow-up are required to be reported..
- Any grade 4 anticipated event not collected on the calendar-driven toxicity or specified event-driven form must **also** be reported.
- Special Situations and Adverse Events of Special Interest (AESIs) must be reported from randomization through the study defined follow-up period.

- Grade 1 CMV infections, as defined in Appendix G, requiring treatment should be reported from randomization through the study defined follow-up period.

SAEs that require reporting will be reported through an expedited AE reporting system via the EDC system. **All SAEs, Special Situations, and AESIs must be reported within 24 hours of knowledge of the event.** Events entered in EDC will be reported using NCI's CTCAE Version 5.0. If there are network outages, a paper copy of the AE form must be completed and emailed to Emmes to initiate Sponsor review. Once the system is available, the event information must be entered into the system.

The Sponsor has a list of events classified as Special Situations. These events are 1) medication error, 2) overdose and 3) pregnancy. These events must be reported, regardless of grade or seriousness, following the reporting process for SAEs.

The Sponsor has a list of AESIs to be reported. These events include any grade of 1) TMA, 2) CRS, 3) CLS, 4) Myalgia, or 5) CK elevation and 6) grade 3 or higher cytopenias. These events must be reported, regardless of grade or seriousness, following the reporting process for SAEs.

Infections of Grade 2 or 3 by Appendix G are collected separately in eClinical as this is a study endpoint; however, should an infection meet the SAE criteria, the infection must also be reported following the SAE reporting criteria outlined above. Grade 1 CMV infections requiring treatment that occur post-randomization will also be reported using the SAE reporting process.

GVHD and underlying disease relapse events are also collected separately in eClinical because they are part of the endpoint analysis. Events of GVHD and underlying disease relapse are not to be reported as AEs/SAEs for this study.

Anticipated AEs will be reported using NCI's CTCAE Version 5.0 at regular intervals as defined on the Form Submission Schedule, including calendar-driven eCRFs (e.g., Toxicity and GVHD) or event-driven eCRFs (e.g., Relapse/Progression, Infection, and Death).

The Data and Safety Monitoring Board (DSMB) will receive expedited reports of all unanticipated and unexpected SAEs upon review by the BMT CTN Medical Monitor and the Xenikos Medical Monitor. Summary reports for all reported SAEs will be reviewed by the DSMB on an annual basis.

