2.5.1.4 Dose and Administration of T-Guard

It is strongly recommended all doses of T-Guard be received while the participant is hospitalized. T-Guard will be administered over 4 hours every 2 calendar days on Days 0, 2, 4, and 6, at a dose of $4\text{mg}/\text{m}^2$ BSA (not to exceed a dose of 10mg). Dosing should be per the following steps:

- Measure the participant's actual body weight (ABW)
- Determine the ideal bodyweight
 - Males IBW = $50\text{kg} + 2.3\text{kg}$ for each inch over 5 feet (or for each 2.5cm over 1.52m)
 - Females IBW = $45.5\text{kg} + 2.3\text{kg}$ for each inch over 5 feet (or for each 2.5cm over 1.52m)
- When the participant's body weight is more than 125% of their IBW, the BSA calculation is based on the adjusted ideal body weight (AIBW; formula 2) as is usual practice for IV treatment (e.g. chemotherapy).

For participants weighing more than 125% of their Ideal Body Weight, calculate the Adjusted Ideal Body Weight: $\text{AIBW} = \text{IBW} + [(0.25) \times (\text{ABW} - \text{IBW})]$

- Use the (adjusted ideal) body weight to determine BSA per the Mosteller calculation

$$BSA(m^2) = \sqrt{\frac{HEIGHT(cm) \times WEIGHT(kg)}{3600}}$$

- Multiply BSA with 4mg/m² as the T-Guard dose. If the participant's BSA is more than 2.5m², the dose calculation should use 2.5m². This dose will be maintained for all infusions (dose adjustments for changes in weight during the treatment period will not be made).

Premedication with antihistaminica (e.g., diphenhydramine 50mg by mouth or 25mg IV, clemastine 2mg IV) is strongly recommended, 20-60 minutes prior to each dose. Premedication with acetaminophen is permitted.

It is recommended that T-Guard be infused via a central catheter using a dedicated line or can be administered via a peripheral line, if needed. If a multi-lumen central venous catheter is used, T-Guard and crystalloid or total parenteral nutrition should be administered through different lumens of the catheter. PK samples should be drawn from the central catheter using a different lumen than the lumen used for infusion.

Before the infusion, connect the syringe with the in-line filter and luer-lock extension tube to a central venous catheter (recommended) or peripheral line. The contents of the syringe will then be administered by means of an automated infusion device, over a period of 4 hours. Once the infusion syringe is empty, the administration tubes should be flushed.

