2.5.1.7 T-Guard Discontinuation

T-Guard treatment must be completed within 14 days of the first study drug dose. Participants who have missed doses may re-start T-Guard provided it is within the 14-day treatment window.

2.5.1.8 aGVHD Progression or Non-response

If additional systemic aGVHD treatment, other than steroids, is added for lack of response or progression, T-Guard treatment must be discontinued and not re-instituted.

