4.2.1 Treatment

Treatment should be initiated as soon as possible after randomization, ideally within 24 hours. A maximum of 72 hours (3 days) after randomization is allowable.

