5.6.12 Incidence of Toxicities

The frequency of Grade 3-5 toxicities per CTCAE Version 5 occurring from randomization until 56 days post-randomization will be tabulated by organ system for each treatment arm. The maximum severity of reported toxicities during that period will also be summarized. The proportions of participants reporting Grade 3-5 toxicities through Day 56 will be compared between arms using logistic regression with adjustment for the stratification factors and for acute GVHD grade at randomization (Grade III vs. IV).

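### Routine AE/SAE collection ends 5 to 8 days earlier for an on-schedule T-Guard participant than for a ruxolitinib participant, and no common cut-off is set for all-AE/SAE tables

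*Combined protocol and SAP*

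**What the plan says.** Section 4.4.4 sets two different rules for routine reporting of all AEs and SAEs. For the experimental arm: "T-Guard arm: all adverse events, including SAEs, must be reported from randomization through 30 days following the last dose of T-Guard". For the ruxolitinib arm, events are to be "reported from randomization through Day 44 (to align with the maximum reporting period for participants in the T-Guard arm").

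Three other places fix the dates. Section 2.5.1.4: "T-Guard will be administered over 4 hours every 2 calendar days on Days 0, 2, 4, and 6". Section 2.5.1.7: "T-Guard treatment must be completed within 14 days of the first study drug dose". Section 4.2.1, on the delay before the first dose: "A maximum of 72 hours (3 days) after randomization is allowable". Section 4.3.1 counts days from randomization as Day 0.

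Section 4.4.4 also lists collection with no arm-specific end date. Related SAEs are reported after the routine window. Unanticipated SAEs, special situations and AESIs (TMA, CRS, CLS, myalgia, CK elevation, Grade 3 or higher cytopenias) are reported through study follow-up. Grade 4 anticipated events not captured on another form are also reported. Section 4.3.2 records infections through Day 180, and toxicities at Days 56, 70, 90 and 180.

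Concomitant-medication recording (Section 4.3.2 and the footnotes to Tables K-1 and K-2) has the same split: last T-Guard dose plus 30 days, against Day 44.

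**The concern.** The control window is fixed at what the protocol takes to be the longest T-Guard window, while the T-Guard window moves with each participant's last dose. Setting one arm at the other arm's maximum does not equalize observation. It makes the control arm the longer-observed arm for everyone except T-Guard participants whose dosing was delayed.

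The length of observation also depends on what happens after randomization, and in one arm only. Someone who stops T-Guard early, for example after suspected anaphylaxis (Section 2.5.1.6) or because other systemic aGVHD therapy was added (Section 2.5.1.8), leaves routine collection soonest. For someone randomized to T-Guard but never dosed, the window is undefined, although the ITT population in Section 5.1.3 includes that person.

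At stake are crude between-arm tables of all AEs and SAEs, including the SAE summaries that Section 4.4.4 sends to the DSMB each year. Chapter 5 sets neither a common cut-off nor an exposure adjustment for such tables. The trial is open-label. Once the routine window closes, an anticipated SAE that falls under none of the other reporting rules is kept only if an investigator who knows the treatment calls it related. T-Guard participants on schedule reach that point earlier.

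**Working it through.** **Inputs.**
- First dose on day s after randomization, s = 0 to 3 (Section 4.2.1).
- Planned fourth dose 6 days after the first (Section 2.5.1.4).
- Last permitted dose 14 days after the first (Section 2.5.1.7).
- Follow-on period of 30 days in the T-Guard arm, and a fixed end at Day 44 for ruxolitinib (Section 4.4.4).

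**The plan's own figure.** Day 44 is reproduced by 14 + 30 = 44. This holds only when the first dose is on Day 0.

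**End of routine T-Guard collection.** One dose: s + 30. On schedule: s + 6 + 30. Stretched to the limit: s + 14 + 30.

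| First dose (day s) | One dose only | On schedule | Stretched to limit |
|---|---|---|---|
| 0 | Day 30 | Day 36 | Day 44 |
| 1 | Day 31 | Day 37 | Day 45 |
| 2 | Day 32 | Day 38 | Day 46 |
| 3 | Day 33 | Day 39 | Day 47 |

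**Gap to ruxolitinib (44 minus the end day).**
- On schedule: 44 − 36 = 8 days down to 44 − 39 = 5 days. The T-Guard window is 36/44 = 82% to 39/44 = 89% of the control window.
- One dose only: 44 − 30 = 14 days down to 44 − 33 = 11 days.
- Stretched: 44 − 44 = 0, to 44 − 47 = −3, so T-Guard is observed up to 3 days longer.

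The latest possible end is 3 + 14 + 30 = Day 47, so Day 44 is not the maximum.

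**What the gap can reach.**

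| Safety output | Window | Affected by the 4.4.4 rule? |
|---|---|---|
| All-AE tables | Last dose + 30 days vs Day 44 | Yes, mainly non-AESI, non-infection events |
| Anticipated, unrelated SAEs, including annual DSMB summaries | Same | Yes |
| AESIs, unanticipated SAEs | Study follow-up, both arms | No |
| Related SAEs | Reported after the window, both arms | No |
| Grade 3-5 toxicities (5.6.12) | Day 56, both arms | Not shown |
| Grade 2-3 infections (5.6.11) | Day 90, both arms | Not shown |
| TMA (5.8.7) | Day 28, both arms | No |
| Comparative mortality monitoring (5.3.2); OS (5.6.1) | Day 60; Day 180 | No |

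Chapter 5 specifies no between-arm test of the all-AE/SAE listing, so the affected outputs are descriptive.

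**The case against.** The strongest defense is that little is lost. The events of most interest with T-Guard are AESIs, which are collected in both arms throughout follow-up. Related and unanticipated SAEs also continue, and every between-arm safety analysis written into Chapter 5 uses one window for both arms. This stands, and it confines the point to descriptive tables of the remaining events.

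Three stronger readings are tempting, and the documents do not support them.

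- A reader might infer that the safety comparison favors T-Guard by construction. The direction is not uniform. Sections 2.5.1.4 and 2.5.1.5 let dosing be delayed for toxicity, which lengthens T-Guard observation to as much as Day 47. The lean toward T-Guard applies to on-schedule participants and early stoppers.
- A reader might infer that the toxicity comparison in Section 5.6.12 is biased, because toxicity recording first appears at Day 56. That section states: "The proportions of participants reporting Grade 3-5 toxicities through Day 56 will be compared between arms". The window is common. The look-back period of the toxicity form is not in the documents, and a form covering Days 0 to 56 is at least as natural a reading. Routine AE rules are also the same in both arms until at least Day 30.
- A reader might scale the Grade 3 or higher rate in Table 1-3 (118/152 by Day 28) at a constant hazard and report a spurious difference of about 5 percentage points: 1 − (34/152)^(36/28) = 85.4% against 1 − (34/152)^(44/28) = 90.5%. That uses the wrong events. The leading Grade 3 or higher events in that table are cytopenias: thrombocytopenia 27%, anemia 22%, platelet count decreased 14%, neutropenia 13%. Cytopenias of that grade are AESIs, so this rule does not cut them off.

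**Conclusion.** The point holds in a limited form. Routine AE/SAE collection depends on the arm. It is 5 to 8 days shorter for a T-Guard participant dosed on schedule, 11 to 14 days shorter after a single dose, and 0 to 3 days longer when dosing is stretched to the limit. The stated reason for Day 44 fails on both counts: it does not align the arms, and it is not the maximum.

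The consequence is under-counting of T-Guard events, for on-schedule participants and early stoppers, in crude tables of all AEs (mainly non-AESI, non-infection events) and of anticipated, unrelated SAEs. The size is certain only in days of observation. Turning it into incidence would need event rates for the truncated categories after Day 30, and the shares of participants who stop early or are delayed. The documents give neither, so no percentage-point bias is claimed.

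The result rests on the dates as written and on between-arm all-AE/SAE tables being produced without truncation or exposure adjustment. The documents neither specify nor rule out either adjustment. This is a cheap improvement, not a threat to the formal safety analyses.

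**What to change.** 1. In Section 4.4.4, collect all AEs and SAEs in the T-Guard arm from randomization through Day 44 or 30 days after the last dose, whichever is later, and through Day 44 for anyone never dosed. Keep Day 44 for ruxolitinib, and remove the description of Day 44 as the T-Guard maximum.
2. In the statistical chapter, add a separate statement that between-arm all-AE/SAE tables, including the DSMB's SAE summaries, use the common Day 0 to 44 window. Do not place it in the Section 5.6.12 endpoint definition, which keeps its Day 56 window.
3. Align concomitant-medication recording in Section 4.3.2 and the footnotes to Tables K-1 and K-2.
4. State the period that the Day 56 toxicity form covers, so that the Section 5.6.12 comparison is beyond question.

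The cost is protocol and eCRF wording, plus 5 to 8 more days of AE recording for on-schedule T-Guard participants and up to 14 for early stoppers. The Day 42 and Day 49 visits already exist in both arms, so no visit is added.

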4.4.5 Procedure in Case of Pregnancy

If a female participant becomes pregnant during the study dosing period or within 90 days from the last dose of study drug, the investigator should report the information through an expedited AE reporting system via the EDC system. The expected date of delivery or expected date of the end of the pregnancy, last menstruation, estimated conception date, pregnancy result, neonatal data and other related information will be requested. If a participant becomes pregnant during the study dosing period, the investigational product will be discontinued.

The investigator will follow the medical status of the mother, as well as the fetus, as if the pregnancy is an SAE and will report the outcome. Additional information regarding the outcome of a pregnancy (which is categorized as an SAE) is mentioned below.

- “Spontaneous abortion” includes miscarriage, abortion, and missed abortion
- Death of an infant within 30 days after birth should be reported as an SAE regardless of

its relationship with the study drug

- If an infant dies more than 30 days after birth, it should be reported if a relationship between the death and intrauterine exposure to the study drug is judged as “possible” by the investigator
- In the case of a delivery of a living newborn, the “normality” of the infant is evaluated at the birth
- Unless a congenital anomaly is identified prior to spontaneous abortion or miscarriage, the embryo or fetus should be assessed for congenital defects by visual examination

Information will be collected at the time of delivery/birth and 180 and 360 days after birth.

CHAPTER 5

